^{*} Overlap weighting was chosen due to the versatility of the methodology. While the method has been subject to simulations and has been used in practice, further testing is underway. If concerns about this methodology arise due to articles published while this study is underway, then inverse probability treatment weighting (IPTW) will be used as the weighting method. If this occurs, IUD insertions will be excluded when there are no comparable patients in one group versus the other (i.e., nonoverlapping propensity scores in the upper and lower tails of the propensity score distribution); patients with propensity scores close to that boundary will be excluded from further analysis. Weighting will then be based on the inverse probability of treatment, and extreme weights (e.g., $> 10^4$) will be excluded (Kurth et al., 2006; Sturmer et al., 2010). This process is called “trimming” and may affect one group more than the other. From the weighted analysis, the average treatment effect within each exposure group will be obtained (Austin, 2013; Austin, 2014). If the exposed and unexposed groups are unbalanced after trimming and application of IPTW, then the logistic regression model will be revised by including interaction terms or higher order terms, and the covariate balance between the two groups will be re-evaluated based on the revised model (Austin, 2011; Rosenbaum and Rubin, 1984).

including interaction terms (e.g., with data source), higher order terms, or transformation of variables, and the covariate balance between the groups overall and within each data source will be re-evaluated based on the revised model (Austin, 2011; Rosenbaum and Rubin, 1984). When satisfactory balance between the exposed and unexposed groups is achieved (e.g., standardized difference < 0.1), the weighting will be incorporated in modeling for confounder-adjusted outcome assessments (Section 9.7.1.3.3). If satisfactory balance is difficult to achieve, especially if there are disparate allocation percentages between groups, matching of patients between groups may be considered.

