for inclusion in propensity score models based on association with the study outcome (Brookhart et al., 2006); thus, analysts will not be blinded to the outcome. Baseline covariates to be considered for inclusion are listed in Sections 3 and 4.6. Categorical variables will be assessed for inclusion based on indicator coding of the categories. Continuous variables (including integer count variables) will be assessed for inclusion as continuous, dichotomous, and categorical (i.e., indicator coded) variables, as appropriate. Covariates will be included in the propensity score model if the crude hazard ratio is greater than 1.11 or less than 0.90. Additional confounders will be selected for inclusion within propensity score models if at least a 10% change in the hazard ratio of the exposure-outcome relationship occurs when adjusting for that variable, including at least a 10% change in any level of a categorical exposure variable relative to the referent group (> 52 weeks postpartum for postpartum period).

From the fitted logistic regression models, propensity scores and the overlap weights (Li et al., 2018) will be estimated for each IUD insertion. Overlap weighting is a relatively new weighting scheme to adjust for confounding effects. Overlap weights belong to a class of balancing weights, including commonly used weights for inverse probability weighting. Li et al. (2018) mathematically proved and verified in simulations that the overlap weights minimize asymptotic variance among balancing weights. Other advantages of overlap weights over inverse probability weighting include perfect balance for means and bounded weights avoiding explosive weights or the need for arbitrary truncation. In addition, the overlap weights focus on the naturally comparable “overlap” population, and therefore propensity score ‘trimming’ for a common support area is not necessary. The overlap weights have been applied in observational studies, for example, Schneider et al. (2001), although the term “overlap weights” was not established at that time.

For dichotomous exposure variables, the propensity score is the probability of being exposed. The propensity score for patient (insertion) i is denoted as $e_i = \Pr(Z_i = 1|X_i)$, where Z_i denotes the exposure (1= exposed, 0 = unexposed), and X_i denotes a vector of baseline covariates. The overlap weight for patient i is defined as follows:

$$w_i = \begin{cases} 1 - e_i, & Z_i = 1 \\ e_i, & Z_i = 0 \end{cases}$$

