The balance across exposure groups will be assessed before and after weighting. The distribution of each variable will be compared between categories of the exposure variable, and balance parameters (i.e., standardized differences) (Austin and Stuart, 2015) will be calculated. Pairwise balance parameters (e.g., pairwise standardized differences) will be used for the categorical exposure variable in which each category will be compared to the referent group (> 52 weeks postpartum for postpartum period). The maximum of the pairwise standardized differences will also be reported. The balance between exposure groups will be assessed overall and within each data source. If the groups are unbalanced on key covariates after application of overlap weighting, then the logistic regression model will be revised by including interaction terms (e.g., with data source), higher order terms, or transformation of variables, and the covariate balance between the groups overall and within each data source will be re-evaluated based on the revised model. When satisfactory balance between the exposed and unexposed groups is achieved, the weighting will be incorporated in modeling for confounder-adjusted outcome assessments (Section 4.1.5). The exposure groups are considered balanced if the standardized difference is less than 0.20 (generally considered small) (McCaffrey et al., 2013). If satisfactory balance is difficult to achieve, which is not expected for overlap weighting, matching of patients between groups may be considered.

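### SAP 4.1.5 accepts balance at a standardized difference below 0.20, twice the protocol's example of 0.1; the looser limit matters within data sources and for functional form, not for pooled means of modelled covariates

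*SAP*

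**What the plan says.** Protocol 9.7.1.3.2 allows the weights into the outcome model once "satisfactory balance between the exposed and unexposed groups is achieved (e.g., standardized difference < 0.1". SAP 4.1.5 states a different figure, as a definition rather than an example: "The exposure groups are considered balanced if the standardized difference is less than 0.20 (generally considered small". It supports 0.20 with a literature citation and does not mention 0.1.

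The figure is an operating rule. The numbered steps in SAP 4.1.5 repeat weighting, balance checking and model revision until the key covariates are balanced. The check has two levels: "The balance between exposure groups will be assessed overall and within each data source". When it fails, the remedies are interaction terms (data source is the example given), higher-order terms or transformations, with matching as a last resort. Once it passes, the weights go into a Cox model with only exposure, site and, where retained, their interaction (notes to SAP Table Layouts 2.1 and 2.2).

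The SAP also says why it expects little trouble: "Other advantages of overlap weights over inverse probability weighting include perfect balance for means and bounded weights".

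**The concern.** The limit decides when refinement stops. A covariate left at a difference of 0.15 goes back for refinement under 0.1 and passes under 0.20. If it passes, the weighted Cox model makes no further adjustment for it.

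The stake is clearest at site level. SAP 6.2.1 tests exposure by data source in the weighted model. If P < 0.05, site-specific hazard ratios are reported and the overall null hypothesis is not tested; otherwise the overall hazard ratio is the primary result. Confounding that differs between sites can distort both the site-specific estimates and the test that chooses between the two reports.

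**Working it through.** Neither document says how much bias a given standardized difference allows, so there is no plan figure to reproduce. The check has three parts.

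**1. Where the limit can bind.** For a binary exposure z, a logistic propensity score e and any term x in the model, the likelihood equations give Σ(z − e)x = 0. Overlap weights are 1 − e for the exposed and e for the unexposed, so this is the same as Σ over exposed of (1 − e)x = Σ over unexposed of e·x. With x = 1 the weight totals are equal, so the weighted means are equal too. This covers only terms in the model. It does not cover the product of a covariate with site, a squared term, or the categories of a variable entered as continuous, unless those are also fitted.

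Simulations, all with assumed coefficients, agree:
- Binary exposure: pooled differences for modelled covariates were zero to machine precision. With an unmodelled site interaction, within-site differences were 0.09 to 0.46 in absolute size.
- Four-level exposure with the correct form: pooled weighted differences were below 0.01, from raw values of 0.30 to 0.74.
- Four-level exposure, 225,000 insertions, unmodelled site-by-covariate log-odds interaction of 0.2: pooled differences were at most 0.002, but within-site differences reached 0.12 and 0.16. These fail 0.1 and pass 0.20.
- Assumed moderate site interactions: about 0.11 to 0.24 within site, up to 0.41 at the smallest.
- Unmodelled functional form: pooled differences in a squared term were 0.08 to 0.26.

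The choice of limit changes the decision only for values between 0.1 and 0.20; larger ones fail either rule.

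**2. Residual bias at each limit.** Perforation is rare (1.3 per 1,000 in Protocol 9.5), so a rare-event approximation serves.
- Continuous covariate: factor = exp(d × ln HR per SD). For an assumed 1.65 per SD, exp(0.20 × 0.501) = 1.105 and exp(0.1 × 0.501) = 1.051.
- Binary covariate: factor = [1 + p1(h − 1)] / [1 + p0(h − 1)], with p1 solved so that the standardized difference equals d. With p0 = 0.40 and h = 2, d = 0.20 gives p1 = 0.499 and 1.499/1.400 = 1.071. For d = 0.1, p1 = 0.449 and 1.449/1.400 = 1.035.
- Range for h = 2 over average prevalences of 5% to 83%: 4% to 7% at 0.20, and 2% to 4% at 0.1.
- Strength one covariate needs to reach 10% at 0.20: 1.61 per SD if continuous, or a hazard ratio of about 2.5 to 2.8 if binary at 11% to 50% prevalence. At 0.1: 2.59 per SD, or about 5.6 to 6.5 at 11% to 30% prevalence.
- Covariates screened out ("Covariates will be included in the propensity score model if the crude hazard ratio is greater than 1.11 or less than 0.90" is the entry rule): at h = 1.11 and d = 0.20, about 1% if binary and 2% per SD if continuous.

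When pooled balance is exact, within-site differences tend to offset in sign. Two sites at +0.20 and −0.20 on the continuous example would have the ratio of their hazard ratios distorted by 1.105² = 1.22. At ±0.1 it would be 1.051² = 1.105.

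**3. What chance alone produces at a small site.** Protocol 9.4.4 gives about 5,700 eligible insertions at the Regenstrief Institute. Applying the pooled 5:70 split (an assumption for this site), 5% is 285 and 70% is 3,990. The standard error of a standardized difference is about √(1/285 + 1/3,990) = 0.061. Since 0.1/0.061 = 1.63, about 10% of truly balanced covariates would exceed 0.1. Expected perforations there are 5,700 × 0.0013 ≈ 7.

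**The case against.** The case for leaving the SAP alone has real force.

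- **Status of 0.1.** The protocol's wording is "e.g., standardized difference < 0.1", an illustration, and Protocol 9.7 leaves analysis detail to the SAP. A reader might infer that a fixed criterion was doubled without being logged. The documents do not support that. SAP Section 7 records edits from SAP version 1.0 to 2.0, and version 1.0, which may already have said 0.20, is not available. What stands is that the two figures differ and are not reconciled.
- **Size in the pooled primary analysis.** A reader might infer a bias of 10% or more in the primary hazard ratio, using the relative risks of 3.3 and 6.1 in Protocol Section 7. Both are breastfeeding effects. In objective 1 breastfeeding is the exposure. In objective 2 it is set to No throughout the referent group, so a modest split against that group cannot arise; that structural imbalance is a separate matter no threshold cures. One binary covariate with hazard ratio 2.3 or less stays below 10% even at 0.20.
- **The 10%-change rule.** A reader might see a contradiction with "Additional confounders will be selected for inclusion within propensity score models if at least a 10% change in the hazard ratio". That rule governs entry to the propensity model. It is not a tolerance for what remains after weighting.
- **Safeguards.** Standardized differences are tabulated and plotted before and after weighting, pooled and by site, and both primary objectives have a covariate-adjusted Cox sensitivity analysis. Imbalance between 0.1 and 0.20 would therefore be seen. It would still not trigger the refinement the SAP itself prescribes.
- **Small sites.** Part 3 shows that a strict 0.1 pass rule would fail by chance at the smallest source, and that adding covariates to a Cox model with few events undercuts the SAP's reason for using propensity scores. This stands, and it shapes the fix.

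**Conclusion.** The point holds in a limited form and is worth fixing, at moderate importance. The SAP's limit is twice the protocol's example and the difference is unreconciled. For pooled means of modelled covariates it should seldom matter. It matters within data sources, for functional form and category distributions, and if matching or the protocol's inverse-probability fallback replaces overlap weighting. There it roughly doubles the tolerated residual bias: about 7% against 4% (binary, hazard ratio 2, prevalence 40%), or 10.5% against 5.1% (1.65 per SD).

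The documents give no covariate hazard ratios for this cohort, so these strengths and prevalences, and the simulation coefficients, are assumptions. The effect on the rejection rate of the exposure-by-site test is not quantified here. Nor does 0.1 guarantee bias below 10%: a continuous covariate at 2.59 per SD would reach it.

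**What to change.** In SAP 4.1.5, replace 0.20 with < 0.1, as in the protocol, and record the change in SAP Section 7. Define it as the trigger for further propensity-model refinement (data-source interactions, higher-order terms, transformations). Apply it overall, pairwise against the referent for the four-level exposure, and within each data source.

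At small sites, where differences above 0.1 can arise by chance, report the residual difference rather than iterate without end. Add a covariate still above 0.1 to the weighted Cox model only as a sensitivity analysis, and only where event counts allow.

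The cost is a wording change and one or two more iterations of the propensity models. No new data are needed.

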Patients will be followed from the time of IUD insertion until the first occurrence of any of the following: uterine perforation, IUD expulsion, IUD removal, indication of IUD reinsertion, indication of new pregnancy, hysterectomy, death, expiration of IUD, disenrollment from the database, or end of the study period. All person-time at risk that meets these criteria will be included, and there will be no requirement for minimum or maximum follow-up time. All IUD insertions occurring with at least 12 months of enrollment before the insertion that are noted within the data sources will be included in the study. The index date will be captured for each insertion, and baseline data will be collected for each index date (Figure 2). The main analyses for the study will

assess only the first observed IUD insertion for each woman in the database. Secondary analyses will be conducted assessing subsequent insertions (i.e., not the first IUD insertion), as recorded in the database. The sequential number of each insertion, as captured in the data for each woman, will be collected and included as a baseline covariate within these secondary analyses.

Figure 2. Covariate data collection around index date

Exposures of postpartum status (based on pregnancy delivery date), breastfeeding status, IUD type, and menorrhagia (as a proxy for indication of use) will be assessed as of the index date of IUD insertion. Outcomes of uterine perforation and IUD expulsion will be assessed beginning on the index date. Baseline data—such as patient demographics, patient characteristics (e.g., personal history of gynecologic conditions such as endometriosis), procedure characteristics, medications, and comorbid conditions (e.g., diabetes)—will be collected from all time in the database before the index date (which will be defined as the day of IUD insertion) and on the index date (Figure 2). Provider characteristics, procedure-related characteristics, and indicators of a difficult insertion will be assessed on the index date (i.e., on the same date or within the same encounter as the index date). The variables to be obtained from each research site are provided in Sections 3.1 through 3.8.

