Separate propensity score models will be developed for exposure-outcome pairings related to breastfeeding status, postpartum period, IUD type, and menorrhagia for uterine perforation and IUD expulsion. The list of propensity score models is provided in Section 9.3. Sections 6.2 and 6.3 includes additional information for specific objectives. In general, the selection of covariates for inclusion in propensity score models will be conducted only using first insertions. The association between baseline covariates and outcomes (crude hazard ratio) will be assessed only using the complete study population, which includes only the first IUD insertion for each woman. No covariate selection will be conducted for *subsequent* insertion models. Instead, for each specific pairing, covariates and terms included in the final propensity score model for first insertions will be included in the propensity score model for subsequent insertions. Additionally, IUD insertion count (the sequential number) may be included in the propensity score model if it is not balanced across exposure groups for *subsequent* insertions. Propensity scores and weights will be estimated from the corresponding propensity score models.

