4.6 Definition of Derived Variables and Subgroups

The variables described in Table 1 will be derived by RTI-HS using the data provided by the four research sites. Since the unit of observation in the data provided by the research partners will be an IUD insertion, these variables will be calculated for each insertion and included in the final dataset. If a woman has more than one eligible insertion in the dataset, the variables will be derived for each insertion using data relevant to that insertion.

Table 1. Definition of Derived Variables

Variable	Definition ^a
Baseline covariates	
IUD insertion count	The number of eligible IUD insertions for the woman as of the index date (including the index insertion). IUD insertion count increases by 1 each time a new index date is identified for the woman
Initial IUD insertion	Indicator variable: If IUD insertion count = 1 then initial IUD insertion = 1 If IUD insertion count > 1 then initial IUD insertion = 0
Difficult insertion	Indicator variable: 1 = Yes if any of the following occur on the index date (or in 7 days before index date for misoprostol): cervical dilation, ultrasound guidance, paracervical block, provider note, use of misoprostol 0 = No if none of the above indicators of difficult insertion are found on the index date
Age tertile	Categorical variable for age based on tertiles (or closest integer cut point [i.e., in years]) for all ages at all first index dates observed within the data
Duration of look-back period	Derived number of days, starting on the date of start of enrollment or first clinical encounter in the EHR database and ending on the index date Duration of look-back period is calculated for each index date
Categorical indicator for provider number of insertions in previous year	Indicator variable: 0 = fewer than 50 provider number of IUD insertions in the 365 days prior to and on the index date, 1 = 50 or more provider number of IUD insertions in the 365 days prior to and on the index date
Provider annualized number of insertions in previous year	Provider number of IUD insertions in previous year divided by provider length of employment in previous year , multiplied by 365

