- ^b Covariates and terms included in the final propensity score model for first insertions will be included in the propensity score model for subsequent insertions. Additionally, IUD insertion count (the sequential number) may be included in the propensity score model if it is not balanced across exposure groups for subsequent insertions.

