RI	xx	xx (xx.x)	xx (xx.x)	xx	xx (xx.x)	xx (xx.x)

[figure not shown]
IUD = intrauterine device.

Generated using xxxx.sas on xxxxxxxx.

[figure not shown]
Programming note 1: Research partners will provide counts for this table.

9.6 Illustration of Continuous Enrollment and Look-Back Time for Kaiser Permanente Sites (KPNC, KPSC, and KPWA)

[figure not shown]
Scenario 1. One IUD Insertion With No Uterine Perforation or IUD Expulsion

Scenario 2. One IUD Insertion With One Uterine Perforation

Scenario 3. Two IUD Insertions, With One IUD Expulsion and One Perforation

Note: if the beginning date of the study period is within the continuous enrollment period (illustrated in the above figures), the beginning date of the study period will be used as the beginning of continuous enrollment. Similarly, if the end date of the study period is within the continuous enrollment period, the end date of the study period will be used as the end of the continuous enrollment.

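### Objectives 18 and 26: the propensity models for subsequent insertions leave out how the previous device ended, so their hazard ratios may carry a bias of unknown size and direction

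*SAP*

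**What the plan says.** SAP 4.1.5 states: "No covariate selection will be conducted for *subsequent* insertion models". Instead, "covariates and terms included in the final propensity score model for first insertions will be included in the propensity score model for subsequent insertions". One addition is allowed: "IUD insertion count (the sequential number) may be included in the propensity score model if it is not balanced across exposure groups". Footnote b of SAP 9.3 repeats both rules for models 10 to 15, which serve objectives 18 and 26. SAP 6.2.2.4 also treats the count as optional.

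SAP Section 3 says something different about the count: it "will be collected and included as a baseline covariate within these secondary analyses". Protocol 9.1 says the same.

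On the candidate list, SAP 4.1.5 says: "Baseline covariates to be considered for inclusion are listed in Sections 3 and 4.6". Nothing in those sections, or in Protocol 9.3.1, describes how an earlier device ended. Expulsion and perforation are defined only as outcomes of the index insertion. Yet the SAP foresees such histories: Scenario 3 in SAP 9.6 is titled "Two IUD Insertions, With One IUD Expulsion and One Perforation".

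**The concern.** Subsequent insertions mix women replacing a device that was removed or had expired with women whose device was expelled or had perforated. If an earlier failure changes the risk with the next device, and if the share of earlier failures differs between exposure groups, the missing variable confounds the hazard ratios for postpartum timing. The same could apply to breastfeeding and IUD type.

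At stake is how these two objectives are read beside the first-insertion results. If the two sets disagreed, nothing pre-specified would show whether timing or device history was the reason.

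**Working it through.** **1. Base inputs.** The documents give no sample size, power or bias figure for objectives 18 and 26, so the only stated figure to check is in Protocol Table 4. For breastfeeding, events = 60,000 × 0.0013 = 78. Power at a hazard ratio of 2.0 = Φ(√(78 × 0.6 × 0.4) × ln 2 − 1.96) = Φ(1.04) = 85.1%, against 85% stated. The inputs reproduce.

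**2. Can the variable enter models 10 to 15 by any route?**

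| Mechanism | Effect |
|---|---|
| Selection rule (crude HR above 1.11 or below 0.90, or at least a 10% change), SAP 4.1.5 | Run on first insertions only, where a previous device's outcome has no values; it can never be selected |
| Insertion count, SAP 4.6 Table 1 | A running number; says nothing about why the device was replaced |
| Rebalancing, SAP 4.1.5 | Adds interactions, higher-order terms or transformations of covariates already considered |
| Robust variance, SAP 6.2.2.4 | Changes the confidence interval, not the point estimate |
| Balance tables, SAP 9.5 Layouts 3.1 and 3.2 | List variables under consideration, so this imbalance would not be displayed |
| Covariate-adjusted sensitivity analysis, SAP 6.2.1 | Primary objectives only |

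**3. Link to timing.** SAP 4.6 sets the 14-week cut at 98 days. If no delivery falls between two insertions, a reinsertion at 98 days or less means that the earlier device was placed and ended within 98 days of the same delivery. That route selects for early failure or removal. The other route is a new delivery after the earlier device ended for any reason. The documents do not give the split.

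**4. Size on assumed inputs.** Let p1 and p0 be the shares of early-postpartum and referent reinsertions that follow an expulsion or perforation, and RR the recurrence ratio. None of the three is in the documents. With a true ratio of 1.00, the unadjusted ratio is approximately

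(1 + p1(RR − 1)) / (1 + p0(RR − 1)).

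| p1, p0 | RR 2 | RR 3 | RR 4 |
|---|---|---|---|
| 0.1, 0.1 | 1.00 | 1.00 | 1.00 |
| 0.2, 0.1 | 1.09 | 1.17 | 1.23 |
| 0.5, 0.1 | 1.36 | 1.67 | 1.92 |
| 0.1, 0.3 | 0.85 | 0.75 | 0.68 |

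For example, at RR 3 with shares 0.5 and 0.1: (1 + 0.5 × 2)/(1 + 0.1 × 2) = 2.0/1.2 = 1.67. The range is 0.75 to 1.67 for RR 2 to 3, and 0.68 to 1.92 once RR 4 is included.

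**5. Does insertion count stand in for it?** A simulation used a true ratio of 1.0, RR 3, shares 0.3 and 0.1, 25% exposed, and a count of three or more in 25% of women with a failed previous device against 10% of the others. The crude ratio was 1.31. Overlap weighting on count alone gave 1.30. Weighting on count plus previous-device outcome gave 0.99, which is 1.00 within simulation error. On these assumed inputs count removes almost nothing.

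**6. Perforation as the outcome.** Protocol 9.5 takes about 90% of insertions as first insertions and expects 225,000 of them. Total = 225,000/0.9 = 250,000, so about 25,000 are subsequent. At 1.3 per 1,000, first insertions yield 225,000 × 0.0013 ≈ 293 perforations in year 1. Even if every one of these women were reinserted, they would be 293/25,000 ≈ 1.2% of subsequent insertions. Shares of 10% to 50% would therefore have to be almost entirely prior expulsions, and RR for objective 18 becomes the effect of a prior expulsion on perforation.

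**The case against.** A reader might infer that the plan inflates these hazard ratios, with a null effect reported at about 1.1 to 1.9. The documents do not support that. Those values arise only if the failure share is assumed higher in the early-postpartum group, and the reverse is plausible:

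- That planned replacement is the usual path in the referent group has no source. KPNC and KPSC data start in 2009 and 2008 (Protocol Table 3), and the last insertion is about 30 April 2018. These two sites hold about 180,000 of 200,700 eligible validation-study insertions, or 90% (Protocol 9.4; most of the counts are stated as minimums).
- With the 5-year expiry that Protocol 9.3.4 sets for Mirena, an expiry replacement is observable only for devices placed by about April 2013. With 10 years for copper, KPNC can show none. The window favours short-interval replacements, which include failures.
- About 70% of first insertions are in the referent category (Protocol 9.5). Without a new delivery, failures there are reinserted in the referent.
- The same-delivery route needs placement, loss and reinsertion all within 98 days.

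It would also be too strong to say that only first-insertion covariates may be used, since the count is permitted.

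The remaining defence is about consequence. Carrying over fixed terms is reasonable when events are few: 25,000 × 0.0013 ≈ 32 perforations. If the first-insertion allocation carried over, power at a hazard ratio of 2.0 would be about 13% for ≤ 6 weeks and 34% for > 6 to ≤ 14 weeks, each against > 52 weeks. Formal testing is confined to the primary objectives, Protocol 9.9 acknowledges residual confounding, and Protocol 9.7.3.4.3 keeps a descriptive fallback if within-woman correlation cannot be handled.

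Most of this stands. It rules out a claim about direction and lowers the weight of objective 18. It does not justify leaving the variable out: the variable would enter an exposure model, which sparse events do not limit, and imprecision does not remove bias. Objective 26 has the same gap.

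**Conclusion.** The point holds as a gap in adjustment and reporting for secondary objectives 18 and 26. Under the SAP as written, the outcome of the previous observed device cannot enter models 10 to 15 and cannot appear in their balance tables. Both primary objectives use first insertions only and are untouched.

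The bias is unknown in size and direction. It is nil if failure shares are equal across groups, upward if the share is higher in the early-postpartum group, and downward if it is higher in the referent. Every figure in step 4 rests on assumed shares and recurrence ratios and illustrates sensitivity; none is an estimate. For objective 18 the concern depends almost wholly on whether prior expulsion affects perforation risk, on which the documents are silent.

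The conflict over the sequential number (mandatory in SAP Section 3 and Protocol 9.1, optional in SAP 4.1.5, 6.2.2.4 and 9.3) is real whatever view is taken of the bias.

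**What to change.** In SAP 4.1.5, 6.2.2.4 and 9.3 footnote b:

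1. Derive the outcome of the woman's previous eligible insertion: expulsion, perforation, or other end (including end not observed). Collapse sparse levels; perforation is likely to need it.
2. Include this variable in propensity models 10 to 15, and show its balance before and after weighting for objectives 18 and 26.
3. Include the sequential number without condition, as SAP Section 3 and Protocol 9.1 already state.
4. Add a sensitivity analysis of objectives 18 and 26 restricted to women whose previous insertion ended without expulsion or perforation.

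The cost is SAP wording, one derived variable, an added balance-table entry and one restricted analysis. No new extraction appears necessary: the dataset is at insertion level, event indicators are derived for each insertion (SAP 4.6), every subsequent insertion has an earlier eligible one in the data, and the insertion count already requires linking a woman's insertions. The restricted analysis will have fewer events and should be presented as supportive.
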